13.4 Reporting to the Drug Provider (Lilly)

Responsibilities of the Principal Investigator and Institution also include:

- to comply with applicable laws, regulations and standards regarding Investigator's and Institution's obligations, as the sponsor of the Study, to collect and report adverse events to regulatory authorities, IRBs, Ethics Committees or other third parties. In addition to the obligations set forth below, Investigator and Institution agree to provide Lilly with a copy of all information Investigator and/or Institution submit to regulators related to any adverse events for the Study Drug that occur during the Study that Investigator and/or Institution have not otherwise provided Lilly;
- to notify Lilly, sub-investigators, and the IRB of any problems involving risk to Study patients and report new safety information to IRBs in accordance with applicable requirements;
- to notify Lilly within fifteen (15) business days of Investigator and/or Institution receiving notification of any "serious" and/or "unexpected" adverse event experienced by a patient participating in the Study and receiving Study Drug that is possibly related, based on Investigator's assessment, to the Study Drug. For purposes of this requirement, "serious" means: (1) death; (2) in-patient hospitalization or prolonged hospitalization; (3) life-threatening; (4) persistent or significant disability or incapacity; (5) congenital anomaly or birth defect; or (6) other serious events that may jeopardize the patient and may require medical or surgical intervention to prevent one of the other five listed outcomes. Serious adverse events should be reported to Lilly using a CIOMS Form or other form acceptable to Lilly. Investigator and Institution further agree to make available promptly to Lilly such

records as may be necessary and pertinent for Lilly to further investigate an adverse event in the Study that is possibly associated with the Study Drug;

Lilly Adverse Event Reporting:

- Local [contact]
Local [contact]

13.5 Reporting to the Drug Provider (Merck)

An adverse event is defined as any untoward medical occurrence in a patient or clinical investigation participant administered a pharmaceutical product and which does not necessarily have to have a causal relationship with this treatment. An adverse event can therefore be any unfavorable and unintended sign (including an abnormal laboratory finding, for example), symptom, or disease temporally associated with the use of a medicinal product or protocol-specified procedure, whether or not considered related to the medicinal product or protocol-specified procedure. Any worsening (i.e., any clinically significant adverse change in frequency and/or intensity) of a preexisting condition that is temporally associated with the use of the Merck's product, is also an adverse event.

Changes resulting from normal growth and development that do not vary significantly in frequency or severity from expected levels are not to be considered adverse events. Examples of this may include, but are not limited to, teething, typical crying in infants and children and onset of menses or menopause occurring at a physiologically appropriate time.

Merck product includes any pharmaceutical product, biological product, device, diagnostic agent or protocol-specified procedure, whether investigational (including placebo or active comparator medication) or marketed, manufactured by, licensed by, provided by or distributed by Merck for human use.

Adverse events may occur during the course of the use of Merck product in clinical trials, or as prescribed in clinical practice, from overdose (whether accidental or intentional), from abuse and from withdrawal.

All AEs, SAEs and other reportable safety events that occur after the consent form is signed but before treatment allocation/randomization must be reported by the investigator if the participant is receiving placebo run-in or other run-in treatment, if the event cause the participant to be excluded from the study, or is the result of a protocol-specified intervention, including but not limited to washout or discontinuation of usual therapy, diet, or a procedure.

- All AEs from the time of treatment allocation/randomization through 30 days following cessation of study treatment must be reported by the investigator.
- All AEs meeting serious criteria, from the time of treatment allocation/randomization through 90 days following cessation of study treatment, or 30 days following cessation of

study treatment if the participant initiates new anticancer therapy, whichever is earlier must be reported by the investigator.

- All pregnancies and exposure during breastfeeding, from the time of treatment allocation/randomization through 120 days following cessation of study treatment, or 30 days following cessation of study treatment if the participant initiates new anticancer therapy must be reported by the investigator.
- Additionally, any SAE brought to the attention of an investigator at any time outside of the time period specified above must be reported immediately by the investigator if the event is considered to be drug-related.

Investigators are not obligated to actively seek AE or SAE or other reportable safety events in former study participants. However, if the investigator learns of any SAE, including a death, at any time after a participant has been discharged from the study, and he/she considers the event to be reasonably related to the study treatment or study participation, the investigator must promptly notify Merck.

13.5.1 Definition of an Overdose for This Protocol and Reporting of Overdose to the Sponsor and to Merck

For purposes of this study, an overdose of pembrolizumab will be defined as any dose of 1,000 mg or greater (≥ 5 times the indicated dose). No specific information is available on the treatment of overdose of pembrolizumab. In the event of overdose, the participant should be observed closely for signs of toxicity. Appropriate supportive treatment should be provided if clinically indicated.

If an adverse event(s) is associated with (“results from”) the overdose of a Merck product, the adverse event(s) is reported as a serious adverse event, even if no other seriousness criteria are met.

If a dose of Merck’s product meeting the protocol definition of overdose is taken without any associated clinical symptoms or abnormal laboratory results, the overdose is reported as a non-serious Event of Clinical Interest (ECI), using the terminology “accidental or intentional overdose without adverse effect.”

All reports of overdose with and without an adverse event must be reported within 24 hours to the Sponsor and within 2 working days hours to Merck Global Safety. (Attn: Worldwide Product Safety; [contact])

13.5.2 Reporting of Pregnancy and Lactation to the Sponsor and to Merck

Although pregnancy and infant exposure during breast feeding are not considered adverse events, it is the responsibility of investigators or their designees to report any pregnancy or lactation in a participant (spontaneously reported to them) that occurs during the study.

Pregnancies and infant exposures during breastfeeding that occur after the consent form is signed but before treatment allocation/randomization must be reported by the investigator if they cause the participant to be excluded from the trial, or are the result of a protocol-specified intervention, including but not limited to washout or discontinuation of usual therapy, diet, placebo treatment or a procedure.

Pregnancies and infant exposures during breastfeeding that occur from the time of treatment allocation/randomization through 120 days following cessation of Sponsor's product, or 30 days following cessation of treatment if the participant initiates new anticancer therapy, whichever is earlier, must be reported by the investigator. All reported pregnancies must be followed to the completion/termination of the pregnancy. Pregnancy outcomes of spontaneous abortion, missed abortion, benign hydatidiform mole, blighted ovum, fetal death, intrauterine death, miscarriage and stillbirth must be reported as serious events (Important Medical Events). If the pregnancy continues to term, the outcome (health of infant) must also be reported.

Such events must be reported within 24 hours to the Sponsor and within 2 working days to Merck Global Safety. (Attn: Worldwide Product Safety; [contact])

13.5.3 Immediate Reporting of Adverse Events to the Sponsor and to Merck

Serious Adverse Events

A serious adverse event is any adverse event occurring at any dose or during any use of investigational product that:

- Results in death;
- Is life threatening;
- Results in persistent or significant disability/incapacity;
- Results in or prolongs an existing inpatient hospitalization;
- Is a congenital anomaly/birth defect;
- Is another important medical event
- Note: In addition to the above criteria, adverse events meeting either of the below criteria, although not serious per ICH definition, are reportable to the Merck in the same timeframe as SAEs to meet certain local requirements. Therefore, these events are considered serious by Merck for collection purposes.
 - Is a new cancer (that is not a condition of the study);
 - Is associated with an overdose.

For the time period beginning when the consent form is signed until treatment allocation/randomization, any serious adverse event, or follow up to a serious adverse event, including death due to any cause that occurs to any participant must be reported within 24 hours to the Sponsor and within 2 working days to Merck Global Safety if it causes the participant to be excluded from the trial, or is the result of a protocol-specified intervention, including but not limited to washout or discontinuation of usual therapy, diet, placebo treatment or a procedure. For the time period beginning at treatment allocation/randomization through 90 days following cessation of treatment, or 30 days following cessation of treatment if the participant initiates new anticancer therapy, whichever is earlier, any serious adverse event, or follow up to a serious adverse event, including death due to any cause whether or not related to the Merck product, must be reported within 24 hours to the Sponsor and within 2 working days to Merck Global Safety.

Additionally, any serious adverse event, considered by an investigator who is a qualified physician to be related to Merck product that is brought to the attention of the investigator at any time following consent through the end of the specified safety follow-up period specified in the paragraph above, or at any time outside of the time period specified in the previous paragraph also must be reported immediately to Merck Global Safety.

All participants with serious adverse events must be followed up for outcome. SAE reports and any other relevant safety information are to be forwarded to the Merck Global Safety [contact]

A copy of all 15 Day Reports and Annual Progress Reports is submitted as required by FDA, European Union (EU), Pharmaceutical and Medical Devices agency (PMDA) or other local regulators. Investigators will cross reference this submission according to local regulations to the Merck Investigational Compound Number (IND, CSA, etc.) at the time of submission. Additionally investigators will submit a copy of these reports to Merck & Co., Inc. (Attn: Worldwide Product Safety; [contact]) at the time of submission to FDA.

13.5.4 Events of Clinical Interest

Selected non-serious and serious adverse events are also known as Events of Clinical Interest (ECI) and must be reported within 2 working days to Merck Global Safety. (Attn: Worldwide Product Safety; [contact]).

For the time period beginning when the consent form is signed until treatment allocation/randomization, any ECI, or follow up to an ECI, that occurs to any participant must be reported within 2 working days to Merck Global Safety if it causes the participant to be excluded from the trial, or is the result of a protocol-specified intervention, including but not limited to washout or discontinuation of usual therapy, diet, placebo treatment or a procedure.

For the time period beginning at treatment allocation/randomization through 90 days following cessation of treatment, or 30 days following cessation of treatment if the participant initiates new anticancer therapy, whichever is earlier, any ECI, or follow up to an ECI, whether or not related to Merck product, must be reported within 2 working days to Merck Global Safety.

Events of clinical interest for this trial include:

1. an overdose of Merck product, as defined in Section 13.5.1 - Definition of an Overdose for This Protocol and Reporting of Overdose to the Sponsor, that is not associated with clinical symptoms or abnormal laboratory results.
2. an elevated AST or ALT lab value that is greater than or equal to 3X the upper limit of normal and an elevated total bilirubin lab value that is greater than or equal to 2X the upper limit of normal and, at the same time, an alkaline phosphatase lab value that is less than 2X the upper limit of normal, as determined by way of protocol-specified laboratory testing or unscheduled laboratory testing.*

*Note: These criteria are based upon available regulatory guidance documents. The purpose of the criteria is to specify a threshold of abnormal hepatic tests that may require an additional evaluation for an underlying etiology.

13.6 Sponsor Responsibility for Reporting Adverse Events

All Adverse Events will be reported to regulatory authorities, IRB/IECs and investigators in accordance with all applicable global laws and regulations.

APPENDIX 1 RECIST 1.1 CRITERIA

RECIST 1.1 will be used as the primary measure for assessment of tumor response, date of disease progression, and as a basis for all protocol guidelines related to disease status (eg, discontinuation of study treatment). Although RECIST 1.1 references a maximum of 5 target lesions in total and 2 per organ, the Sponsor allows a maximum of 10 target lesions in total and 5 per organ, if clinically relevant to enable a broader sampling of tumor burden. All patients will have their BEST RESPONSE on study classified as outlined below:

Complete Response (CR)

Disappearance of all target lesions. Any pathological lymph nodes (whether target or non target) must have reduction in the short axis to <10mm.

Partial Response (PR)

At least a 30% decrease in the sum of diameters of target lesions, taking as reference the baseline sum LD.

Stable Disease (SD)

Steady state of disease. Neither sufficient shrinkage to qualify for PR nor sufficient increase to qualify for PD.

Progressive Disease (PD)

At least a 20% increase in the sum of diameters of measured lesions taking as references the smallest sum of diameters recorded since the treatment started. In addition to the relative increase of 20%, the sum must also demonstrate an absolute increase of at least 5 mm. Appearance of one or more new lesions will also constitute progressive disease.

Response Duration

Response duration will be measured from the time measurement criteria for CR/PR (whichever is first recorded) are first met until the first date that recurrent or progressive disease is objectively documented, taking as reference the smallest measurements recorded since the treatment started.

Stable Disease Duration

Stable disease duration will be measured from the time of start of therapy until the criteria for progression are met, taking as reference the smallest measurements recorded since the treatment started.

APPENDIX 2: DESCRIPTION OF THE IRECIST PROCESS FOR ASSESSMENT OF DISEASE PROGRESSION

Assessment at Screening and Prior to RECIST 1.1 Progression

Until radiographic progression based on RECIST 1.1, there is no distinct iRECIST assessment.

Assessment and Decision at RECIST 1.1 Progression

In participants who show evidence of radiological PD by RECIST 1.1 the Investigator will decide whether to continue a participant on study treatment until repeat imaging is obtained (using iRECIST for participant management (see Table 1 and Figure 1). This decision by the Investigator should be based on the participant's overall clinical condition.

Clinical stability is defined as the following:

- Absence of symptoms and signs indicating clinically significant progression of disease
- No decline in ECOG performance status
- No requirements for intensified management, including increased analgesia, radiation, or other palliative care

Any participant deemed clinically unstable should be discontinued from study treatment at site-assessed first radiologic evidence of PD, and is not required to have repeat tumor imaging for confirmation of PD by iRECIST.

If the Investigator decides to continue treatment, the participant may continue to receive study treatment and the tumor assessment should be repeated 4 to 8 weeks later to confirm PD by iRECIST, per Investigator assessment. I

Tumor flare may manifest as any factor causing radiographic progression per RECIST 1.1, including:

- Increase in the sum of diameters of target lesion(s) identified at baseline to $\geq 20\%$ and ≥ 5 mm from nadir
 - Please note: the iRECIST publication uses the terminology “sum of measurements”, but “sum of diameters” will be used in this protocol, consistent with the original RECIST 1.1 terminology.
- Unequivocal progression of non-target lesion(s) identified at baseline
- Development of new lesion(s)

iRECIST defines new response categories, including iUPD (unconfirmed progressive disease) and iCPD (confirmed progressive disease). For purposes of iRECIST assessment, the first visit showing progression according to RECIST 1.1 will be assigned a visit (overall) response of iUPD, regardless of which factors caused the progression.

At this visit, target and non-target lesions identified at baseline by RECIST 1.1 will be assessed as usual.

New lesions will be classified as measurable or non-measurable, using the same size thresholds and rules as for baseline lesion assessment in RECIST 1.1. From measurable new lesions, up to 5 lesions total (up to 2 per organ), may be selected as New Lesions – Target. The sum of diameters of these lesions will be calculated, and kept distinct from the sum of diameters for target lesions at baseline. All other new lesions will be followed qualitatively as New Lesions – Non-target.

Assessment at the Confirmatory Imaging

On the confirmatory imaging, the participant will be classified as progression confirmed (with an overall response of iCPD), or as showing persistent unconfirmed progression (with an overall response of iUPD), or as showing disease stability or response (iSD/iPR/iCR).

Confirmation of Progression

Progression is considered confirmed, and the overall response will be iCPD, if ANY of the following occurs:

- Any of the factors that were the basis for the initial iUPD show worsening
 - For target lesions, worsening is a further increase in the sum of diameters of ≥ 5 mm, compared to any prior iUPD time point
 - For non-target lesions, worsening is any significant growth in lesions overall, compared to a prior iUPD time point; this does not have to meet the “unequivocal” standard of RECIST 1.1
 - For new lesions, worsening is any of these:
 - An increase in the new lesion sum of diameters by ≥ 5 mm from a prior iUPD time point
 - Visible growth of new non-target lesions
 - The appearance of additional new lesions
- Any new factor appears that would have triggered PD by RECIST 1.1

Persistent iUPD

Progression is considered not confirmed, and the overall response remains iUPD, if:

- None of the progression-confirming factors identified above occurs AND
- The target lesion sum of diameters (initial target lesions) remains above the initial PD threshold (by RECIST 1.1)

Additional imaging for confirmation should be scheduled 4 to 8 weeks from the scan on which iUPD is seen. This may correspond to the next visit in the original visit schedule. The

assessment of the subsequent confirmation scan proceeds in an identical manner, with possible outcomes of iCPD, iUPD, and iSD/iPR/iCR.

Resolution of iUPD

Progression is considered not confirmed, and the overall response becomes iSD/iPR/iCR, if:

- None of the progression-confirming factors identified above occurs, AND
- The target lesion sum of diameters (initial target lesions) is not above the initial PD threshold.

The response is classified as iSD or iPR (depending on the sum of diameters of the target lesions), or iCR if all lesions resolve.

In this case, the initial iUPD is considered to be pseudo-progression, and the level of suspicion for progression is “reset”. This means that the next visit that shows radiographic progression, whenever it occurs, is again classified as iUPD by iRECIST, and the confirmation process is repeated before a response of iCPD can be assigned.

Management Following the Confirmatory Imaging

If repeat imaging does not confirm PD per iRECIST, as assessed by the Investigator, and the participant continues to be clinically stable, study treatment may continue and follow the regular imaging schedule. If PD is confirmed, participants will be discontinued from study treatment.

NOTE: If a participant has confirmed radiographic progression (iCPD) as defined above, but the participant is achieving a clinically meaningful benefit, an exception to continue study treatment may be considered. In this case, if study treatment is continued, tumor imaging should continue to be performed following the intervals as outlined above.

Detection of Progression at Visits After Pseudo-progression Resolves

After resolution of pseudo-progression (ie, achievement of iSD/iPR/iCR), iUPD is indicated by any of the following events:

- Target lesions
 - Sum of diameters reaches the PD threshold ($\geq 20\%$ and ≥ 5 mm increase from nadir) either for the first time, or after resolution of previous pseudo-progression. The nadir is always the smallest sum of diameters seen during the entire trial, either before or after an instance of pseudo-progression.
- Non-target lesions
 - If non-target lesions have never shown unequivocal progression, their doing so for the first time results in iUPD.

- If non-target lesions had shown previous unequivocal progression, and this progression has not resolved, iUPD results from any significant further growth of non-target lesions, taken as a whole.
- New lesions
 - New lesions appear for the first time
 - Additional new lesions appear
 - Previously identified new target lesions show an increase of ≥ 5 mm in the new lesion sum of diameters, from the nadir value of that sum
 - Previously identified non-target lesions show any significant growth

If any of the events above occur, the overall response for that visit is iUPD, and the iUPD evaluation process (see Assessment at the Confirmatory Imaging above) is repeated. Progression must be confirmed before iCPD can occur.

The decision process is identical to the iUPD confirmation process for the initial PD, except in one respect. If new lesions occurred at a prior instance of iUPD, and at the confirmatory scan the burden of new lesions has increased from its smallest value (for new target lesions, their sum of diameters is ≥ 5 mm increased from its nadir), then iUPD cannot resolve to iSD or iPR. It will remain iUPD until either a decrease in the new lesion burden allows resolution to iSD or iPR, or until a confirmatory factor causes iCPD.

Additional details about iRECIST are provided in the iRECIST publication.[46]

**APPENDIX 3: EASTERN COOPERATIVE ONCOLOGY GROUP (ECOG)
PERFORMANCE STATUS SCALE ASSESSMENT**

ECOG Performance Status Scale	
Grade	Descriptions
0	Normal activity. Fully active, able to carry on all pre-disease performance without restriction.
1	Symptoms, but ambulatory. Restricted in physically strenuous activity, but ambulatory and able to carry out work of a light or sedentary nature (e.g., light housework, office work).
2	In bed <50% of the time. Ambulatory and capable of all self-care, but unable to carry out any work activities. Up and about more than 50% of waking hr.
3	In bed >50% of the time. Capable of only limited self-care, confined to bed or chair more than 50% of waking hr.
4	100% bedridden. Completely disabled. Cannot carry on any self-care. Totally confined to bed or chair.
5	Dead.

**APPENDIX 4: COMMON TERMINOLOGY CRITERIA FOR ADVERSE EVENTS V5.0
(CTCAE)**

The descriptions and grading scales found in the revised NCI Common Terminology Criteria for Adverse Events (CTCAE) version 5.0 will be utilized for adverse event reporting. (<http://ctep.cancer.gov/reporting/ctc.html>)

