6.3.5 Tumor Imaging on Study

The first on-study imaging assessment should be performed at 6 weeks (42 days \pm 7 days) from the date of allocation. Subsequent tumor imaging should be performed every 6 weeks (42 days \pm 7 days) or more frequently if clinically indicated. After 6 months, participants who remain on treatment will have imaging performed every 12 weeks (84 days \pm 7 days). Imaging timing should follow calendar days and should not be adjusted for delays in cycle starts. Imaging should continue to be performed until disease progression is identified by the Investigator.

Objective response should be confirmed by a repeat imaging assessment. Tumor imaging to confirm PR or CR should be performed at least 4 weeks after the first indication of a response is observed. Participants will then return to regular scheduled imaging every 6 weeks, starting with the next scheduled imaging time point. Participants who receive additional imaging for confirmation do not need to undergo the next scheduled tumor imaging if it is less than 4 weeks later; tumor imaging may resume at the subsequent scheduled imaging time point.

PROTOCOL NUMBER: OSU-19132

Per iRECIST (Appendix 2), disease progression should be confirmed by the site 4 to 8 weeks after first radiologic evidence of PD in clinically stable participants as defined by Appendix 2 (Note- if patient is receiving clinical benefit, oligoprogressive CNS disease that can be controlled with local therapy such as stereotactic radiation, may continue on treatment beyond progression with PI approval. Ramucirumab should be held for 2 weeks prior to radiation. Patient can have radiation for CNS oligoprogression as long as ramucirumab is held for 4-6 weeks afterwards. Ramucirumab can be restarted after this time if the patient is asymptomatic, clinically stable and this is considered appropriate by the investigator.). Participants who have unconfirmed disease progression may continue on treatment at the discretion of the Investigator until progression is confirmed by the site provided they have met the conditions detailed in Section 9.2.1.6. Participants who receive confirmatory imaging do not need to undergo the next scheduled tumor imaging if it is less than 4 weeks later; tumor imaging may resume at the subsequent scheduled imaging time point, if clinically stable. Participants who have confirmed disease progression by iRECIST, as assessed by the site, will discontinue study treatment.

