8.4 Prohibited Medication

Participants are prohibited from receiving the following therapies during the Screening and Treatment Phase (including retreatment for post-complete response relapse) of this trial:

- Antineoplastic systemic chemotherapy or biological therapy
- Immunotherapy not specified in this protocol
- Chemotherapy not specified in this protocol
- Investigational agents other than pembrolizumab
- Chronic antiplatelet therapy, including aspirin, nonsteroidal anti-inflammatory drugs (NSAIDs, including ibuprofen, naproxen, and others), dipyridamole or clopidogrel, or similar agents is not permitted. Once-daily aspirin use (maximum dose 325 mg/day) is permitted.
- Radiation therapy
 - Note: Radiation therapy to the brain may be allowed after consultation with the PI for patients receiving clinical benefit. See section 6.3.5. . Ramucirumab therapy should be temporarily discontinued for 2 weeks prior to starting radiation. However,

starting radiation sooner is permissible if the investigator considers that the benefits outweigh the risks for the patient. Patient can have radiation for CNS oligoprogression as long as ramucirumab is held for 4-6 weeks afterwards. Ramucirumab can be restarted after this time if the patient is asymptomatic, clinically stable and this is considered appropriate by the investigator.

- Live vaccines within 30 days prior to the first dose of study treatment and while participating in the study. Examples of live vaccines include, but are not limited to, the following: measles, mumps, rubella, varicella/zoster, yellow fever, rabies, BCG, and typhoid vaccine. Seasonal influenza vaccines for injection are generally killed virus vaccines and are allowed; however, intranasal influenza vaccines (eg, FluMist®) are live attenuated vaccines and are not allowed.
- Systemic glucocorticoids for any purpose other than to modulate symptoms from an event of clinical interest of suspected immunologic etiology. The use of physiologic doses of corticosteroids may be approved after consultation with the Sponsor.

Participants who, in the assessment by the investigator, require the use of any of the aforementioned treatments for clinical management should be removed from the study. All treatments that the Investigator considers necessary for a participant's welfare may be administered at the discretion of the Investigator in keeping with the community standards of medical care.

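### Sections 6.3.5 and 8.4 let treatment continue through brain radiation where Appendix 2 and Table 1 call for stopping, and Appendix 2 can then label the irradiated progression pseudo-progression

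*Combined protocol and SAP*

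**What the plan says.** **Continuation.** Section 6.3.5 provides that, in a patient with clinical benefit, "oligoprogressive CNS disease that can be controlled with local therapy such as stereotactic radiation, may continue on treatment beyond progression with PI approval". Section 8.4 lists radiation as prohibited but adds a note: "Radiation therapy to the brain may be allowed after consultation with the PI for patients receiving clinical benefit", with a reference back to 6.3.5.

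**Stopping.** Appendix 2 sets three conditions for clinical stability. The third is "No requirements for intensified management, including increased analgesia, radiation, or other palliative care". It then directs: "Any participant deemed clinically unstable should be discontinued from study treatment at site-assessed first radiologic evidence of PD". Table 1 (Section 1.5.5) likewise says to discontinue in its clinically unstable column at first progression.

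**Scoring.** Under Appendix 2, the first RECIST 1.1 progression becomes unconfirmed progression (iUPD) whatever caused it. A repeat scan follows 4 to 8 weeks later. If no confirming factor is present and the sum of the initial target lesions is not above the progression threshold, the status becomes iSD, iPR or iCR. Appendix 2 adds: "In this case, the initial iUPD is considered to be pseudo-progression". Suspicion of progression is then reset.

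**Use of the criteria.** Section 1.5.4 and Appendix 1 make RECIST 1.1 the primary measure for response and progression date. Section 1.5.5 has the investigator use iRECIST for treatment decisions, and Section 9.1.1 evaluates the response rate by both criteria.

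**The concern.** There are two linked problems. First, the plan gives no single answer on whether a patient who needs brain radiation stays on treatment. Handling could differ between investigators, and between sites if the expansion foreseen in Section 3.1.4 goes ahead.

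Second, for patients who stay on, the resolution rule was written for tumor flare that settles by itself. It does not ask whether the lesion that caused the progression has since been irradiated. Control achieved by radiation can therefore be recorded as pseudo-progression, with progression status cleared. At stake are the iRECIST progression record, any description of pseudo-progression under this combination, and later decisions to continue treatment. No passage says how a locally treated lesion is to be scored.

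**Working it through.** The plan states no figure to reproduce on this point. The check traces one patient through the text and then applies the Appendix 2 rule to worked cases.

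**1. One patient, four passages.** Take a patient with clinical benefit whose scan shows a new brain lesion requiring stereotactic radiation.

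- Section 6.3.5: may continue, with PI approval.
- Section 8.4: brain radiation may be allowed after PI consultation. The paragraph closing the list says that patients who need a listed treatment should be removed from the study, and radiation is on that list.
- Appendix 2: the third stability condition fails, so the patient is unstable and should stop.
- Table 1: unstable column, discontinue.

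No passage settles which applies. The note in 6.3.5 sits inside a sentence limited to progression "in clinically stable participants as defined by Appendix 2", which is the definition this patient fails. For patients with unconfirmed progression, 6.3.5 then points to Section 9.2.1.6 for the conditions of continuing. That section does not exist; 9.2 is the sample size justification. The clinical-benefit exception in Appendix 2 applies only after confirmed progression. Table 1 lets an unstable patient restart after a favourable repeat scan, but that comes after the decision at first progression.

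**2. The resolution rule on assumed cases.** Assume a baseline target sum of 100 mm and a nadir of 60 mm. Progression needs an increase of at least 20% and at least 5 mm from nadir: 60 × 1.20 = 72 mm and 60 + 5 = 65 mm, so the threshold is 72 mm. A rise of 5 mm or more in the target sum from the iUPD scan would confirm progression.

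| Case | Sum at first PD | Sum at repeat scan | Other findings | Appendix 2 result |
|---|---|---|---|---|
| a. New brain lesion, irradiated | 60 | 60 | Lesion stable or smaller | Resolved: pseudo-progression, reset |
| b. Brain lesion is a baseline target, irradiated | 75 | 64 (not above 72) | None | Resolved: pseudo-progression, reset |
| c. As b | 75 | 74 (above 72; change −1) | None | Stays iUPD |
| d. As a | 60 | 60 | Irradiated lesion grows, or another new lesion | Confirmed (iCPD) |

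Relabelling is therefore conditional. It occurs when radiation achieves the local control that 6.3.5 presupposes, nothing else worsens, and the target sum is not above the threshold.

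**3. What this does to response.** At nadir the sum is (100 − 60)/100 = 40% below baseline, past the 30% needed for PR before the brain event.

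- Case a: the sum is 60 with or without radiation, because new lesions are summed separately. Radiation cannot create the iPR.
- Case b: the sum moves from (100 − 75)/100 = 25% to (100 − 64)/100 = 36% below baseline and crosses the 30% line. An irradiated baseline target can thus contribute directly to an iPR. If this patient's earlier response was confirmed, no responder is added.
- Indirect route: radiation averts iCPD and a response in other lesions is first reached later.

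**4. Timing.** Ramucirumab is held 2 weeks before radiation (8.4 permits a shorter interval) and 4 to 6 weeks after, so 2 + 4 = 6 to 2 + 6 = 8 weeks in all. If the hold starts at first progression and radiation is brief, the repeat scan at 4 to 8 weeks can fall while ramucirumab is off. That makes radiation a more plausible explanation of local control.

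**5. Scale.** The documents give no CNS progression rate. Purely as an assumption, 5% to 20% of 34 patients is 1.7 to 6.8, or about 2 to 7 irradiated. That is a ceiling, since cases c and d are not relabelled. Each added iRECIST responder among 34 would be 1/34 = 2.9 percentage points.

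**The case against.** **It is a specific exception.** The note in 6.3.5 is narrow (CNS oligoprogression, benefit, local control, PI approval), and 8.4 repeats it. It reads naturally as an exception to a general definition, and Appendix 2 bases the decision on overall clinical condition. This may well be the intent. But neither Appendix 2 nor Table 1 carries the exception or points to it, and 6.3.5 relies on the very definition it would override. The need to reconcile stands.

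**The effect on response.** A reader might infer that radiation would turn true CNS progressions into responses and inflate the response and disease-control rates in every irradiated patient. The documents do not support that. A patient already in confirmed PR adds no responder. A new brain lesion stays outside the baseline target sum that separates iSD from iPR. Disease control could rise only if the CNS event came before any scan showing SD or better. Growth or a further new lesion still gives iCPD.

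**Progression date.** A reader might also infer that progression-free survival is at risk. Section 1.5.4 and Appendix 1 give the date to RECIST 1.1, and iUPD is itself assigned at the first RECIST 1.1 progression, so that visit is identified.

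**The cited source may cover it.** Appendix 2 defers further detail to the iRECIST publication, which I cannot check. If it has a rule for locally treated lesions, the protocol should state it, because the text as written leads sites to the opposite result.

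**Excluding responses after radiation is debatable.** This stands: blanket exclusion would discard responses defined by unirradiated lesions outside the brain.

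**Conclusion.** The conflict over continuation is established from the text alone; which clinical rule should prevail is not a matter for this review. The scoring gap also holds, for patients kept on treatment who meet both resolution conditions. Its main effects are on iRECIST progression status, pseudo-progression labels and iRECIST-based continuation decisions. iRECIST response could be inflated directly only through an irradiated baseline target, or indirectly if radiation averts confirmed progression and a response is first reached afterwards. RECIST 1.1 response and the first progression date are unaffected, given the primacy stated in Section 1.5.4 and Appendix 1. The number of patients whose iRECIST result would change cannot be computed. The point should be corrected, but it does not threaten the RECIST 1.1 analysis.

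**What to change.** 1. Reconcile Sections 6.3.5 and 8.4 with the stability definition in Appendix 2 and with Table 1, so that one rule decides whether a patient needing CNS radiation continues. Add cross-references and correct the pointer to Section 9.2.1.6.
2. State in Appendix 2 that a lesion given local therapy after iUPD is non-evaluable as evidence that iUPD has resolved or for reaching iPR or iCR, that such events are not labelled pseudo-progression, and what visit status these patients carry.
3. Add a CRF flag for locally treated lesions, with the treatment date.
4. Report iRECIST responses first reached after on-study radiation separately, and show the iRECIST response rate with and without them.

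The cost is protocol wording, one CRF item and one extra line in the response table. The iRECIST response rate may be slightly lower. No patients or procedures are added.
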